A planned study visit schedule will be established at Baseline/Day 1 (first day of treatment) for all participants. All subsequent scheduled visits will be calculated based on the Day 1 visit date. The mandatory post-Baseline visits of the study are Week 4, Week 8, Week 12, Week 16 and Week 48. After Week 16, the treatment visit intervals will be determined by the Investigator, based on the patient’s disease activity (see [Section 6.7.2](#)). All efforts should be made to adhere to all scheduled visits and assessments as outlined in the assessment schedule ([Table 8-1](#)).

A \pm 7-day visit window is allowed, except for Baseline/Day 1, should the participant be unable to return per scheduled visit. All efforts should be made to revert back to the planned visit schedule taking into consideration the restrictions on the minimum treatment interval for the study treatment, i.e. two consecutive injections should be at least 21 days apart.

For a given protocol visit (except for Baseline), assessments can be performed on two consecutive days, provided both days are within the \pm 7-day visit window.

Treatment is intended to be administered on the day of study visit, or if this is not possible, within 3 days after the study visit at which the per-protocol assessments have taken place (except Baseline, in which case study treatment administration should occur within the next 24 hours). For all visits, efficacy assessments ([Section 8.3](#)) and safety assessments ([Section 8.4](#)) should be performed prior to any administration of study treatment.

Missed or rescheduled visits should not lead to automatic discontinuation. Participants who prematurely discontinue the study for any reason should be scheduled for a visit as soon as possible, at which time all of the assessments listed for the final visit will be performed.

If the COVID-19 pandemic limits or prevents on-site study visits, study treatment could not be administered and other study assessments may not be performed. Alternative methods of safety monitoring may be implemented. Depending on local regulations, site capabilities and patient's visit status in the study, phone calls or virtual contacts (e.g. teleconsult) can be performed for safety follow-up for the duration of the pandemic, until it is safe for the participant to visit the site again.

Table 8-1 Assessment schedule

Period	Screening	Treatment						End of Study
Visit Name	Screening*	Baseline Day 1	W4	W8	W12	W16	Treatment visits	W48*

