For what concern the LOCF approach reported in the study protocol, this approach will be maintained for the predictors to be included in the analysis of the primary endpoint since the focus is on the first visits (from baseline to Week 16) and all enrolled patients should perform these visits independently of treatment regimen that will be followed by each patient. For the secondary endpoints, LOCF approach will not be applied because after Week 16 each patient will have different scheduled of visits based on treatment regimen. The LOCF approach can be considered only until Week 16 but (1) for OCTA the number of missing data will lead to most data imputed than the one observed, (2) for SD-OCT the approach is applied in the analysis of primary endpoint, (3) for BCVA the LOCF approach will be provided until Week 16, (4) for HAD and EQ-5D-5L questionnaires the LOCF approach will not be applied since only two assessments of these questionnaires are planned in the study.

As performed for interim analysis, all analysis will be conducted on Safety population since during the interim analysis, in which all enrolled patients were considered (see section 6.6 for further details), the FAS and Safety populations include the same set of patients since per definitions of the study protocol, the FAS considered all enrolled patients who completed the baseline visit and all of them are treated and consequently all of them belong to Safety population.

The evaluation of prevalence of anxiety and depression will be performed only based on HAD questionnaire and not based in terms of treatment that patients could have received for anxiety/depression.

The following additional analysis will be included:

- SD-OCT parameters at baseline and type of predominant lesion will be also analyzed according to BCVA groups and CST groups based on changes at Week 12 in patients who performed Week 16 and were still on treatment at this timepoint.
- A graphical representation of BCVA ETDRS score and CST by means of spaghetti plot will be provided.
- Analyses on CST and BCVA will be also performed on patients with BCVA ETDRS score lower than 69 letters at baseline.

| | |
|--|----------------------------------|
| | Statistical Analysis Plan |
| | Sponsor: Novartis |
| | Protocol: CRTH258AIT04 |

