SRF, sub-RPE fluid, hemorrhage, CRT and/or OCTA parameters and/or 3-field CFP). A first disease activity assessment is to be performed at Week 16, as recommended in Beovu® SmPC. In participants without disease activity, treatment every 12 weeks (q12w) should be considered. In patients with DA, treatment every 8 weeks (q8w) should be considered. Disease activity will be first assessed at Week 16 and then at each subsequent scheduled q12w/q8w treatment visit. In participants on q12w regimen with disease activity at any of these visits, a q8w treatment regimen should be considered. In participants on q8w regimen without disease activity for two consecutive treatment visits in the opinion of the Investigator, the re-allocation to a q12w regimen should be considered. Figure 2.3.1-1 provides a graphical summary of the study drug administration during the study.

Figure 2.3.1-1: Treatment regimen

Regardless of treatment administration, Baseline, Week 4, Week 8, Week 12, Week 16 and Week 48 visits are mandatory for all participants. The timepoints of the other treatment visits will depend on the treatment regimen of each participant (q12w/q8w).

For all participants, the last potential study treatment will be at the Week 44 visit or at the Week 48 visit, according to the different treatment regimen implemented.

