3.5. Sample Size and Power Estimation

The sample size calculation is based on the assumption of an expected percentage of participants who have maintained the q12w regimen up to Week 48 equal to 56%, as derived from the HAWK study, and the hypothesis of a maximum percentage of not-fluid free participants out of these q12w-regimen participants at Week 48 equal to 18%. Therefore, the percentage of responders, defined as fluid-free participants who have maintained a q12w stable regimen up to Week 48, could range between 56% to 46%.

[figure not shown]
Considering a percentage of responders of 56% and a maximum width of the 95% confidence interval of 12%, 263 patients should be enrolled. Applying the rules of thumb, with 263 patients and a percentage of responders of 56%, a maximum number of 12 covariates can be included in the multivariate regression model (Harrell, 2015). As shown in Figure 2.5-1, the precision of the estimate remains stable around 12%, considering a percentage of responders ranging between 56% to 46%. Similar considerations can be made with a number of covariates that remains equal to 12.

Finally, to account for a screening failure rate of 12%, a total of approximately 300 participants should be screened in order to enroll 263 evaluable participants.

The sample size calculations were performed with nQuery 7.0.

| | |
|--|----------------------------------|
| | Statistical Analysis Plan |
| | Sponsor: Novartis |
| | Protocol: CRTH258AIT04 |

[figure not shown]
Figure 2.5-1: Precision of the estimate scenario

Since the enrolment was closed with less than 263 enrolled patients, the precision of the 95% CI will be re-computed based on the effective number of patients evaluable for the primary endpoint of the study.

Based on interim analysis, 122 enrolled patients will be available and consequently, the Figure above is recomputed according to the effective number of enrolled patients and provided below in Figure 2.5-2:

Figure 2.5-2: Precision of the estimate scenario re-computed

Based on different scenario of expected proportion between 46% to 56% and the effective number of 122 enrolled patients, the maximum width that can be observed will be of 17.74%.

| | |
|--|---|
| | Statistical Analysis Plan |
| | Sponsor: Novartis Protocol: CRTH258AIT04 |

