4. DEFINITIONS AND GENERAL METHODOLOGY

4.1. General Methodology

Statistical tables, listings and analyses will be produced using SAS® release 9.4 (64 bit) or later (SAS Institute, Inc., Cary, NC, USA).

The data from all sites will be pooled and summarized.

Continuous data will be summarized with mean, standard deviation (SD), median, Q1, Q3, minimum and maximum. Categorical data will be presented by absolute and relative frequencies (n and %) or contingency tables. The percentage calculation will be based on total values (i.e., count will be shown also in the missing category, unless otherwise specified).

Unless stated otherwise, a two-sided alpha level 0.05 will be considered. No alpha level adjustment will be carried out for primary and secondary outcome variables, unless otherwise specified.

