For quantitative variables (i.e., CST (μm)), absolute changes from baseline will be computed and summarized at each visit. A paired t-test or Wilcoxon signed rank test, based on data distribution, will be used to test the difference at each time point vs Baseline. A spaghetti plot of CST values at each timepoint will be provided by type of predominant CNV lesion (of note, 'UNG/Q' and 'UNG/P' evaluation of predominant CNV lesion will be considered in a unique category 'Ungradable').

CST will also be described considering only patients with BCVA ETDRS score lower than 69 letters at baseline in terms of descriptive statistics together with absolute changes from baseline and by means of spaghetti plot.

For the qualitative variables IRF, SRF, sub-RPE, SHRM, ORT and ELM integrity loss a shift table of each post-baseline visit vs Baseline will be provided. A McNemar test will be used to test the difference at each post-baseline visit vs baseline. Of note, shift tables will be provided considered only patients for whom baseline and post-baseline value are both available (i.e., parameter considered equal to 'No' or 'Yes') and moreover, the measurements of these qualitative parameters in center 1 mm and at foveal center will not be considering for shift tables.

Data handling rules

An observed approach will be considered for all the analysis.

Sensitivity of secondary analysis

Not applicable.

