6.3.2.3. Best corrected visual acuity (BCVA)

Definition

The visual acuity is assessed by means of Best corrected visual acuity (BCVA). BCVA measurements will be taken in a sitting position using Early Treatment Diabetic Retinopathy Study (ETDRS) like visual acuity testing charts at an initial testing distance of 4 meters. The ETDRS chart has been established as the gold standard for objective VA measurement in clinical trials and consists of 14 rows of 5 letters each, for a total of 70 letters. A higher score represents better vision. BCVA will be assessed in the study eye at every study visit and in the fellow eye at Screening and Week 48. Only assessment on the study eye will be considered in the analysis.

Analysis methodology

BCVA ETDRS score in the study eye will be summarized at each visit by means of descriptive statistics for continuous variable together with absolute changes from baseline. A paired t-test or Wilcoxon signed rank test, based on data distribution, will

| | |
|--|----------------------------------|
| | Statistical Analysis Plan |
| | Sponsor: Novartis |
| | Protocol: CRTH258AIT04 |

be used to test the BCVA ETDRS score difference at each time point vs Baseline. A spaghetti plot of BCVA ETDRS score at each timepoint will be provided by type of predominant CNV lesion (of note, 'UNG/Q' and 'UNG/P' evaluation of predominant CNV lesion will be considered in a unique category 'Ungradable').

In addition, considering each post-baseline visit, the proportion of patients with improvement of at least 5, 10 and 15 letters in BCVA ETDRS score (i.e., absolute change greater or equal to 5, 10 and 15, respectively) will be provided. Similarly, the proportion of patients with worsening of at least 5, 10 and 15 letters in BCVA ETDRS score (i.e., absolute change less or equal to -5, -10 and -15, respectively) will be summarized.

The same analyses will be also repeated focusing on patients with BCVA ETDRS score at baseline lower than 69 letters.

Data handling rules

Firstly, an observed approach will be considered for all the analysis and the LOCF approach will be also applied but focusing only until Week 16 since after this timepoint the scheduled of visits will be different for each patient according to treatment regimen assigned.

Sensitivity of secondary analysis

Not applicable.

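### The SAP's reason for dropping imputation does not apply at Week 48, so Week 48 BCVA, CST and fluid results rest on observed values only, with no sensitivity analysis and a conflicting rule in SAP 4.4.2

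*SAP*

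**What the plan says.** Protocol 12.4.4 plans LOCF, mainly for the secondary endpoints, together with an observed-data approach. SAP 1.1 changes this: "For the secondary endpoints, LOCF approach will not be applied because after Week 16 each patient will have different scheduled of visits". It allows LOCF up to Week 16 only.

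The endpoint sections follow SAP 1.1:

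- **BCVA (SAP 6.3.2.3):** "Firstly, an observed approach will be considered for all the analysis and the LOCF approach will be also applied but focusing only until Week 16".
- **CST and SD-OCT fluid (SAP 6.3.2.2):** "An observed approach will be considered for all the analysis". The shift tables and McNemar tests use only patients graded yes or no at both baseline and the visit.
- **Fluid resolution by visit (SAP 6.3.2.4):** the base is patients with fluid at baseline who had an SD-OCT at that visit.

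Each of these sections marks sensitivity analysis as not applicable.

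Two other statements bear on this. SAP 3.3.1 says: "Regardless of treatment administration, Baseline, Week 4, Week 8, Week 12, Week 16 and Week 48 visits are mandatory for all participants". SAP 4.4.2, the general missing-data section, still states that LOCF will handle missing data for the secondary endpoints, with an as-observed approach as well.

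For early leavers, Protocol section 8 says: "Participants who prematurely discontinue the study for any reason should be scheduled for a visit as soon as possible". SAP 3.4 repeats this. All final-visit assessments are to be done at that visit.

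**The concern.** An argument from differing schedules justifies not imputing a value at a visit that was never planned for that patient. It covers Weeks 20 to 44, where the regimen decides which visits take place. At Week 48 a visit is planned for everyone, so a missing value is truly missing. It may reflect study exit, a missed visit, or an image that could not be graded or was not graded.

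Week 48 is also where the endpoint definitions in SAP section 2 end for BCVA and SD-OCT. The paired tests, the 5/10/15-letter gain and loss rates and the fluid results at that visit carry the one-year message. With no control arm, any selection in who has a value passes straight into the reported change.

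The SAP recognises the risk elsewhere. In 6.3.1 it accepts that leaving out patients with missing data can cause selection bias, and it plans an inverse-probability-weighted analysis, but only for the primary outcome. Separately, 4.4.2 and 6.3.2 give different instructions, so two programmers could produce different Week 48 tables.

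**Working it through.** **1. The plan's own figures.** SAP 3.5 states: "Considering a percentage of responders of 56% and a maximum width of the 95% confidence interval of 12%, 263 patients should be enrolled". With a Wald interval, n = (2 × 1.95996 × √(0.56 × 0.44) / 0.12)² = 262.93, rounded up to 263. For the 122 patients enrolled it says "the maximum width that can be observed will be of 17.74" per cent. The width is 2 × 1.95996 × √(0.25/122) = 17.74% at a proportion of 50%. Both figures reproduce. They concern the primary responder proportion; no stated figure covers the Week 48 secondary changes. The 12% in that section is a screening failure rate, not drop-out.

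**2. The rules side by side.**

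| Place | Rule for secondary endpoints | Does it cover a missing Week 48 value? |
|---|---|---|
| Protocol 12.4.4 | LOCF plus observed | Yes |
| SAP 1.1 | No LOCF after Week 16, because schedules differ | Reason does not apply: Week 48 is mandatory |
| SAP 4.4.2 | LOCF plus as observed | Yes, contradicting 1.1 and 6.3.2 |
| SAP 6.3.2.2 | Observed only | No |
| SAP 6.3.2.3 | Observed; LOCF to Week 16 only | No |
| SAP 4.4.3 | Drop-outs enter with available assessments | Not without a rule placing exit visits at Week 48 |

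**3. Bias of an observed mean.** Let d be the fraction missing, m₁ the mean change in patients with a value and m₂ the mean change in those without. The all-patient mean is (1 − d)m₁ + d·m₂, so the observed mean exceeds it by d(m₁ − m₂). The documents give none of these three quantities. Assume an observed gain of 6 letters and d = 10%:

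- m₂ = 0: 0.9 × 6 + 0.1 × 0 = 5.4, and 6/5.4 = 1.11
- m₂ = −5: 0.9 × 6 + 0.1 × (−5) = 4.9
- m₂ = −10: 0.9 × 6 + 0.1 × (−10) = 4.4, and 6/4.4 = 1.36

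These cases assume that the missing patients do worse. Without that assumption, the bias d(m₁ − m₂), in units of benefit, is:

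| d | Missing do 5 better | Same | 5 worse | 10 worse |
|---|---|---|---|---|
| 10% | −0.5 | 0 | +0.5 | +1.0 |
| 20% | −1.0 | 0 | +1.0 | +2.0 |
| 30% | −1.5 | 0 | +1.5 | +3.0 |

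**4. Rates.** If no missing patient gained the letters, the observed gain rate is 1/(1 − d) times the all-patient rate: 1.11 at d = 10% and 1.25 at d = 20%. For fluid, assume 60% are dry among those observed. The all-patient proportion then lies between 0.6(1 − d) and 0.6(1 − d) + d: 54% to 64% at 10% missing, 48% to 68% at 20%, and 42% to 72% at 30%.

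**5. Would restoring LOCF cure it?** Not reliably. Take d = 20%, an observed mean of +6, and leavers whose last value is +8 but whose true Week 48 value is +2. LOCF gives 0.8 × 6 + 0.2 × 8 = 6.4, and the true mean is 0.8 × 6 + 0.2 × 2 = 5.2. The observed mean of 6.0 is closer than LOCF.

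**The case against.** The strongest reply is that the observed analysis is not an analysis of completers. Protocol 9.1.1 lists unsatisfactory effect and retinal vasculitis or vascular occlusion as reasons to stop study treatment, not to leave the study. Such patients should keep attending to Week 48, and those who attend are in the tables. This stands, and a reader who infers a completers-only analysis goes too far. It does not remove the problem. Continued attendance is at the discretion of the investigator or the participant, and abbreviated contacts need collect only treatments and adverse events.

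Second, a missing imaging value need not mean that the patient left. SAP 1.1 reports many ungradable SD-OCT and OCTA values, and SAP 6.3.1 notes images left ungraded because the instrument was not certified. This also stands, and it is why the causes must be reported separately.

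Third, fluid is partly covered elsewhere. The primary q12w fluid-free outcome counts leavers and treatment stoppers as failures, and time to sustained dryness is censored at the last SD-OCT. Those analyses are not in question. The gap is in the Week 48 shift tables and the by-visit resolution proportion. Nor does the primary rule set a standard for mean changes, since it follows from an outcome that requires stable q12w treatment to Week 48.

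Last, these are secondary single-arm summaries without alpha adjustment. That limits the weight of the point but does not answer it.

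**Conclusion.** The point holds in a limited form. The stated reason for dropping imputation fails at Week 48, and the Week 48 BCVA, CST and fluid changes have neither a missing-data method nor a sensitivity analysis. The use of exit-visit data is undefined, and SAP 4.4.2 contradicts 1.1 and 6.3.2. The contradiction and the failed reason can be read directly from the documents and rest on no assumption.

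A reader might infer that the one-year effect is overstated. The documents do not show that. They give no drop-out rate, expected gain or outcome in leavers. Over the assumed grid the bias runs from −1.5 to +3.0 units. Favourable bias is plausible if patients leave because of poor effect or ocular events; the example of 6 letters against 5.4 to 4.4 assumes 10% missing with changes of 0 to −10.

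Nor do the documents show that severe losses after inflammation are the values that will be absent. The 5.3% and 3.2% in Protocol 4.5 are rates of all inflammation-related events in women and men in the earlier phase III trials. They are not rates of vision loss or study exit, so they cannot supply a count of missing losses.

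The change should be made, but it does not affect the primary analysis.

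**What to change.** 1. Reconcile SAP 1.1, 4.4.2 and 6.3.2, and limit the differing-schedule reason to Weeks 20 to 44.
2. For each endpoint, report how many patients have a Week 48 value and why the others do not, separating study exit, missed visit, and ungradable or ungraded image.
3. State how exit-visit assessments are used in the Week 48 analyses.
4. For BCVA and CST, add beside the observed results a mixed model for repeated measures on the mandatory visits (Baseline, Weeks 4, 8, 12, 16 and 48), including Safety Set patients with any post-baseline value.
5. Add sensitivity analyses that keep all Safety Set patients in the denominator:
   - 5/10/15-letter gain rates with missing counted as not gained;
   - loss rates using the exit-visit value where there is one, with best and worst bounds for the rest;
   - Week 48 fluid resolution with missing counted as not dry, plus best and worst bounds, among all Safety Set patients with fluid at baseline (the group SAP 6.3.2.4 starts from).

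The cost is SAP wording and a few tables on data already collected. The Week 48 figures may look slightly less favourable. The mixed model assumes missing at random, which the data cannot confirm; the bounds do not need that assumption, but they cover only the rates.

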2. STUDY OBJECTIVES AND ENDPOINTS

| OBJECTIVES | VARIABLES | ENDPOINTS |
|--|---|---|
| 
Primary objective(s):
 
The primary objective is to assess the predictive value of early anatomical parameters measured by multimodal imaging from Baseline to Week 16, in brolucizumab-treated participants with wAMD who present fluid resolution (i.e. absence of IRF and SRF) at Week 48 and have maintained the q12w treatment regimen up to Week 48 after the loading phase, defined also as fluid-free response (q12w fluid-free participants), compared with participants under a more frequent regimen and/or not fluid-free at Week 48.
 | 
To define the outcome of interest:
 
 • Intraretinal fluid (IRF) based on SD-OCT at Week 48 • Subretinal fluid (SRF) based on SD-OCT at Week 48 • Regimen assigned and followed during the study 
The following variable will be considered as predictive factors:
 
 1. Basal CNV lesion type (i.e., Type of predominant CNV lesion) 2. SD-OCT Parameters at each visit from Baseline to Week 16: 
 • Sub-retinal pigment epithelium (sub-RPE) fluid • Subretinal Hyperreflective Material (SHRM) • Outer Retinal Tubulation (ORT) • ELM integrity loss in center 1 mm • Type of PED • Center Subfield Thickness (CST) | 
Primary endpoint(s):
 
Early predictive factors of fluid-free response, which is defined as the absence of IRF and SRF (assessed by SD-OCT) at Week 48 in patients with a stable q12w treatment regimen up to Week 48 after the loading phase.
 
The variables considered as potential predictive factors in the statistical model will be selected among the following qualitative and quantitative anatomical parameters:
 
 1. Basal CNV lesion type (i.e., Type of predominant CNV lesion), as assessed by SD-OCT at Baseline and FA, ICGA and CFP at Screening 2. Parameters assessed by SD-OCT at each visit from Baseline to Week 16, of which the main are presence/absence of sub-RPE fluid, subretinal hyperreflective material (SHRM), outer retinal tubulation, status of the External Limiting Membrane (ELM) and measurement of central retinal thickness (CRT) and type of PED |

| | |
|--|----------------------------------|
| | Statistical Analysis Plan |
| | Sponsor: Novartis |
| | Protocol: CRTH258AIT04 |

| OBJECTIVES | VARIABLES | ENDPOINTS |
|--|---|--|
| 
Secondary objective(s):
 
1. To evaluate the effect of brolucizumab on the evolution of qualitative and quantitative OCTA parameters of wAMD from Baseline to Week 48
 | 
1. OCTA qualitative parameters graded by CRC:
 
 • Branching vessels • Peripheral Anastomotic Arcades • Vascular Loops • Dark Halo • Presence CNV lesion and its involvement of the foveal center 
1. OCTA quantitative parameters graded by CRC:
 
 • CNV flow size including Total CNV lesion area (mm²) and Greatest linear diameter of lesion (mm) • Vessel density of the lesion including CNV vascular density (%) | 
Secondary endpoint(s):
 
1. Change in OCTA features assessed by qualitative (branching vessels, peripheral anastomotic arcades, vascular loops and dark halo) and quantitative criteria (CNV flow size, and vessel density) from Baseline up to Week 48
 |
| 
2. To evaluate the effect of brolucizumab on the evolution of qualitative and quantitative SD-OCT parameters of wAMD from Baseline to Week 48
 | 
2. SD-OCT qualitative parameters graded by CRC:
 
 • Intraretinal fluid (IRF) including the subcategories: (1) IRF in center 1 mm and (2) IRF at foveal center. • Subretinal fluid (SRF) including the subcategories (1) SRF in center 1 mm and (2) SRF at foveal center. • Sub-retinal pigment epithelium (sub-RPE) fluid including the subcategory sub-RPE in center 1 mm | 
2. Change in SD-OCT features assessed by qualitative (IRF, SRF, sub-RPE fluid, status of ELM, SHRM, outer retinal tubulation and presence and type of PED) and quantitative criteria (CRT) from Baseline up to Week 48
 |

| | |
|--|---|
| | Statistical Analysis Plan |
| | Sponsor: Novartis Protocol: CRTH258AIT04 |

| OBJECTIVES | VARIABLES | ENDPOINTS |
|--|--|--|
| | 
 • Subretinal Hyperreflective Material (SHRM) including the subcategories (1) SHRM in center 1 mm and (2) SHRM at foveal center. • Outer Retinal Tubulation (ORT) including the subcategory ORT in center 1 mm • Status of the ELM as an indicator of retinal integrity considering ELM integrity loss in center 1 mm • Presence and type of PED 
2. SD-OCT quantitative parameters graded by CRC:
 
 • Center Subfield Thickness (CST) | |
| 3. To evaluate the effect of brolucizumab on the evolution of functional parameters of wAMD from Baseline to Week 48 | 3. BCVA ETDRS Score | 3. Change in BCVA from Baseline up to Week 48 |
| 4. To evaluate the effect of brolucizumab on sustained dryness from Baseline to Week 48 | 4. SD-OCT dates, Intraretinal fluid (IRF) and Subretinal fluid (SRF) | 
4. Time to reach sustained dryness of the study eye, as defined by the absence of IRF and SRF for at least 2 consecutive visits and for at least 3 consecutive visits
 
4. Cumulative incidence of sustained dryness of the study eye, i.e. the absence of IRF and SRF for at least 2 consecutive visits and for at least 3 consecutive visits
 |

| | |
|--|---|
| | Statistical Analysis Plan |
| | Sponsor: Novartis Protocol: CRTH258AIT04 |

| OBJECTIVES | VARIABLES | ENDPOINTS |
|--|---|--|
| 5. To evaluate the reasons underlying the Investigators' choice of brolucizumab treatment regimen (q21w or q8w) at Week 16 | 
5. Parameters considered to assess the presence of disease activity:
 
 • BCVA • Leakage at FA/ICGA • Central Subfield Thickness (CST) at SD-OCT • Intraretinal fluid (IRF) at SD-OCT • Subretinal fluid (SRF) at SD-OCT • Subretinal pigment epithelium (sub-RPE) fluid at SD-OCT • Retina Pigment Epithelial Detachment volume at SD-OCT • Central Retinal Thickness (CRT) • Subretinal hyperreflective material (SHRM) at SDOCT • CNV size at OCTA • Vessel density at OCTA • Vessel morphology at OCTA • Hemorrhage at CFP • Other | 5. Determinants in the Investigator's choice of brolucizumab dosing regimen (q12w or q8w) at Week 16 (i.e. BCVA, IRF, SRF, sub-RPE fluid, presence of hemorrhages, CRT, OCTA anatomical parameters and/or 3-field CFP) |
| 6. To evaluate anxiety/depression in patients with wAMD treated with brolucizumab | 6. HADS questionnaire | 6. Change in Hospital Anxiety and Depression Scale (HADS) scores from Baseline to Week 48 |
| 7. To evaluate quality of life in patients with wAMD treated with brolucizumab | 7. EuroQol-5D-5L questionnaire | 7. Change in EuroQol-5D-5L (EQ-5D-5L) scores from Baseline to Week 48 |

| | |
|--|---|
| | Statistical Analysis Plan |
| | Sponsor: Novartis Protocol: CRTH258AIT04 |

| OBJECTIVES | VARIABLES | ENDPOINTS |
|--|-------------------|--|
| 8. To assess the safety and tolerability of brolucizumab | 8. Adverse Events | 8. Incidence of Ocular and Non-ocular AEs throughout the study |

